# **Treatment of Relapsed or Refractory Acute Lymphoblastic Leukemia (ALL) with CMC-544 (Inotuzumab Ozogamycin), with or without Later Addition of Rituximab**

## **1.0 Objectives**

- To evaluate the efficacy of treatment with CMC-544 with or without later rituximab in patients with relapsed or refractory ALL.
- To evaluate the side effects of the treatment.

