## **5.0 Treatment Plan**

### **5.1 General**

This is an open label, phase II study. The design will evaluate single agent efficacy of CMC-544 as initial treatment, first in patients  $\geq 16$  years and then in patients less than 16 years. If stable disease or worse after 2 courses, CMC-544 will continue with the addition of rituximab, as detailed below.

CMC-544 will be provided by Wyeth Corporation. Any unused or expired drug will be destroyed per institutional policy.

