### **5.2 Treatment Schema**

**5.2.1** The first 3 patients  $\geq 16$  years and the first 3 patients  $< 16$  years will receive CMC-544 at a dose of  $1.3 \text{ mg/m}^2$  IV over 1 hour (+/- 15 minutes) during Course 1, and  $1.8 \text{ mg/m}^2$  IV over 1 hour (+/- 15 minutes) during Course 2 and subsequently. In all other patients, if there are no safety issues, CMC-544 will be given at a dose of  $1.8 \text{ mg/m}^2$  IV over 1 hour (+/- 15 minutes) about every 4 weeks. This will constitute a course of therapy. Courses will be repeated about every 4 weeks (range 3-6 weeks).

Courses can be started earlier, every 2 weeks if evidence of rapid progression after approval by the principal investigator.

**5.2.2** In a second phase (see 2.4), 20 patients will be treated with weekly CMC-544. CMC-544 will be given at 0.8 mg/m^2 IV over 1 hour ( $\pm$  15 minutes) on Day 1, 0.5 mg/m^2 IV over 1 hour ( $\pm$  15 minutes) on Day 8, and 0.5 mg/m^2 IV over 1 hour ( $\pm$  15 minutes) on Day 15. Weekly doses can be given at  $\pm$  1 day. Course may be repeated every 3 weeks.

Recommended premedication before CMC-544: acetaminophen 650 mg orally, diphenhydramine 10-25 mg IV, hydrocortisone 25 mg IV. Modifications to this premedication are also allowed.

Prophylaxis for tumor lysis syndrome may be administered at the discretion of the treating physician.

**5.2.3** If stable disease, no improvement or progression after 2 courses of CMC-544, patients may continue on CMC-544 at the same dose every 3-4 weeks, with the addition of rituximab 375 mg/m^2 IV over 2-6 hours every 3-4 weeks. The first dose of rituximab will be given as a slow infusion over 6-8 hours depending on reactions and side effects. It will be given on Day 1 and CMC-544 on Day 2. Subsequent courses of CMC-544 and rituximab may be given on the same day; CMC-544 will be given at least 2-4 hours after completion of rituximab. Courses can be started earlier, every 2 weeks if evidence of

rapid progression after approval by the principal investigator. In the second phase of weekly CMC-544, rituximab will be given on Day 1 and CMC-544 on Day 2 of the first dose; with subsequent weekly doses, both will be given weekly, rituximab preceding CMC-544. The weekly dose of rituximab will be 375 mg/m^2.

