Infusion 1 of rituximab will be over 6-8 hours following infusion rate increases as per hospital standards. Infusions 2-6 of rituximab may be run at faster rates of 2-6 hours as indicated by side effects and per hospital standards.

**5.2.4** Patients achieving response, defined as CR or CRi, or partial remission (PR) may continue therapy for up to 8 cycles (about 8-12 months of therapy). Patients with progression at any time or without objective response after 3 cycles will be taken off study.

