### **5.3 Treatment Duration and Dose Adjustments**

Patients will receive 2 courses of CMC-544. If CR, complete remission without platelet recovery (CRi), or PR is documented, whichever comes first, then continue CMC-544. If a patient does not achieve a CR, CRi, or PR then add rituximab as under 5.2.

Patients who achieve a CR, CRi, or PR may receive up to a total of 8 cycles of therapy depending on leukemia response and resolution of toxicities. Subjects who demonstrate a CR or CRi after 1 or 2 cycles of therapy will receive a maximum of 4 cycles of therapy. Subjects who are in a CR or CRi after 3-4 cycles may receive a maximum of 2

additional cycles of therapy after achieving a CR or CRI. After a total of 4 cycles, patients will be assessed for the need of the 4 additional cycles based on response and liver toxicities with the previous 4 cycles. Cycles are repeated about every 4 weeks (range 3-6 weeks) depending on leukemia response, resolution of toxicities, and recovery of hematopoiesis.

Patients receiving subsequent cycles (cycles 2-8) will be treated at the same dose level if grade  $\leq$  2 non-hematologic toxicity has occurred and if they have experienced a favorable response of their leukemia (decrease in peripheral blood or marrow blasts). Re-treatment will only occur upon recovery to < grade 2 non-hematologic or baseline toxicity. If they have non-hematologic toxicity of  $\geq$  grade 3 and a favorable response to therapy, additional cycles of therapy at 25% dose reduction of CMC-544 may be considered after this is discussed with and approved by the Principal Investigator. No dose reductions for rituximab are needed.

Patients who develop CNS leukemia while on study will be removed from the study and receive CNS-directed therapy, except where such patients have a positive response to therapy in which case they will continue on study after discussion with the Principal Investigator.

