## **11.0 Statistical Considerations**

A total of up to 60 patients will be treated. The primary endpoint for efficacy is response which is defined as CR, CRI or PR.

The method of Thall [1995] will be employed to perform interim futility monitoring.

The trial will be stopped early if:  $\Pr[\theta > 0.20 | \text{data}] < 0.10$ . Where  $\theta$  denotes the response rate. That is, given the outcomes from the patients who have already been evaluated, if we determine that there is less than a 10% chance that the response rate is 20% or more, we will stop the trial for futility. We assume a prior distribution of  $\theta \sim \text{beta}(1,1)$ . Stopping boundaries corresponding to this probability criterion are to terminate the trial if:

(# patients with CR, CRi, or PR) / (# patients evaluated)

≤ 0/10, 1/17, 2/24, 3/31, 4/37

The operating characteristics for the futility monitoring rule are shown in the following table.

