### **Operating Characteristics for Stopping Rule (PL=0.10)**

Clinical Scenario	Early Stopping Probability	Achieved Sample Size (25th, 50th, 75th percentile)
Response rate is 0.1	0.79	10, 17, 37
Response rate is 0.2	0.24	40, 40, 40
Response rate is 0.3	0.044	40, 40, 40

Reference:

Thall, Peter F., Simon, R. and Estey, E.H. "Bayesian sequential monitoring designs for single-arm clinical trials with multiple outcomes," Statistics in Medicine 14:357-379, 1995.

**11.1** In an update of the data on October 6, 2010, 12 of the first 21 patients treated (57%) had achieved CR or Cri. This was achieved with minimal drug related side effects, and allowed several patients to proceed safely to allogeneic stem cell transplant. These data are very encouraging and if consistent in a larger number of patients may show that single agent CMC-544 therapy is superior to standard combination intensive chemotherapy with regard to safety and efficacy. We therefore propose to increase the total number of patients treated to 60 patients to allow a more accurate assessment of the response rate and to define more precisely predictive

factors for response and outcome with CMC-544 therapy. The analysis of predictive factors for response, durability of response, and survival will be conducted using standard statistical methods, and will be descriptive, for the purpose of guiding future large scale and pivotal trials with CMC-544 in ALL.

**11.2** Following the update of January 7, 2011, it is proposed to treat 20 patients with a weekly schedule of CMC-544, to gain experience with efficacy and toxicity. This portion of the study should protect against an overall response rate < 40%. Therefore the study will stop early if the number of responses over number evaluable is: 0/7, 1/10, 2/14, and 3/17. Otherwise a total of 20 patients will be treated. The response and toxicity evaluations will be descriptive.

**11.3** Following an update on December 2, 2011, the weekly schedule was assessed to demonstrate equal or better efficacy and perhaps less toxicity than the single dose every 3-4 weeks. In the first 15 evaluable patients, 8 (53%) achieved marrow CR. An additional 20 patients will be treated for a total of 40 patients to assess more precisely the response and toxicity rates with the weekly schedule.

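### The any-time response rate measures CMC-544 with or without rituximab, while 5.1 and 11.1 speak of the single agent; separately, 5.2.4 contradicts 5.1 and 5.2.3 on progressing patients

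*Combined protocol and SAP*

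**What the plan says.** **Target.** The efficacy objective in Section 1.0 is "To evaluate the efficacy of treatment with CMC-544 with or without later rituximab in patients with relapsed or refractory ALL". Section 5.1 puts it differently: "The design will evaluate single agent efficacy of CMC-544 as initial treatment". Section 11.1 takes the October 2010 result (12 of 21 with CR or CRi) and says that such data, if they hold in more patients, "may show that single agent CMC-544 therapy is superior to standard combination intensive chemotherapy with regard to safety and efficacy".

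**Endpoint.** Section 11: "The primary endpoint for efficacy is response which is defined as CR, CRI or PR". Section 8 defines each category by counts and marrow findings and attaches no day, cycle or treatment condition.

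**Adding rituximab.** Section 5.3: "If a patient does not achieve a CR, CRi, or PR then add rituximab as under 5.2". Section 5.2.3: "If stable disease, no improvement or progression after 2 courses of CMC-544, patients may continue on CMC-544", with rituximab added. Section 5.1 likewise adds rituximab for stable disease or worse after two courses.

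**Progression.** Section 5.2.1: "Courses can be started earlier, every 2 weeks if evidence of rapid progression after approval by the principal investigator". Section 5.2.4: "Patients with progression at any time or without objective response after 3 cycles will be taken off study". Section 9 lists progressive disease among the reasons for which the investigator may, not must, remove a patient.

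**The concern.** There are two targets and one endpoint. A patient who fails two courses of CMC-544, receives rituximab and then responds counts as a responder. That is right for the strategy but wrong for a statement about CMC-544 alone. The updates in 2.4, 2.5, 2.6 and 11.1 do not say whether any response followed rituximab, so a reader cannot tell which rate is being shown. This matters because 11.1 uses the rate to support enlargement to 60 patients and to guide later pivotal trials. Rituximab is also given every 3-4 weeks in the first phase and weekly in the second, so an unsplit comparison of schedules could mix CMC-544 schedule with rituximab exposure.

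The second problem is one of instructions. For the same progressing patient the protocol both requires removal and permits further treatment. The choice decides who receives more drug and who can still become a responder.

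**Working it through.** **1. The plan's own figures.** With a beta(1,1) prior, the posterior after r responses in n patients is beta(1+r, 1+n-r). Pr(rate > 0.20) is 0.086, 0.099, 0.098, 0.093 and 0.099 at 0/10, 1/17, 2/24, 3/31 and 4/37, and above 0.10 with one patient fewer in each case, so the boundaries reproduce. An exact binomial recursion with a maximum of 40 patients gives early-stopping probabilities of 0.783, 0.240 and 0.045 at true rates of 0.1, 0.2 and 0.3. The table has 0.79, 0.24 and 0.044. The arithmetic is sound; the question is what the rate measures.

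**2. Window for a response after rituximab.** Rituximab starts after course 2, and 5.2.4 removes patients without objective response after 3 cycles. That ordinarily leaves about one rituximab cycle for a first response. The limit is indirect: it is a treatment rule rather than an endpoint window, and 5.3 also provides for patients in CR or CRi after 3-4 cycles.

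**3. Size of the overstatement.** Pooled rate minus CMC-544-alone rate = (1 - p) x f x r, where p is the CMC-544-alone rate, f the share of non-responders given rituximab, and r their response rate after the add-on. None of these is in the documents. I assume p 45-55%, f 25-100% and r 5-20%.

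- Lowest: 0.45 x 0.25 x 0.05 = 0.6 points (p = 55%).
- Middle: 0.50 x 0.50 x 0.10 = 2.5 points.
- Highest: 0.55 x 1 x 0.20 = 11 points (p = 45%).

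In 21 patients this is 21 x 0.006 = 0.1, 21 x 0.025 = 0.5 and 21 x 0.11 = 2.3 responses.

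**4. Sampling error, exact 95% intervals.**

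- 12/21 = 57% (34.0-78.2%)
- 18/32 = 56% (37.7-73.6%)
- 8/15 = 53% (26.6-78.7%)
- assumed 20/40 = 50% (33.8-66.2%), about 16 points either side

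Even the highest value in step 3 is smaller than this.

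**5. Futility.** The observed 12/21, 18/32 and 8/15 lie far above the nearest boundaries (1/17, 3/31 and, for the weekly schedule, 2/14). By the same recursion, the stopping probability at a true rate of 0.53 is 0.06% under the Section 11 rule and 1.2% under the 11.2 rule (20 patients). At 0.57 it is 0.02% and 0.6%. This holds only at rates of this size. At an assumed CMC-544-alone rate of 10%, with 10% of all non-responders responding after the add-on, the counted rate is 0.10 + 0.90 x 0.10 = 0.19, and early stopping falls from 0.78 to 0.28. The trial is not in that region.

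**6. The progression rules.** Take a patient who progresses after course 2. Sections 5.1 and 5.2.3 continue CMC-544 and add rituximab. Section 5.2.4 takes the patient off study. Section 9 leaves it to the investigator. A patient with rapid progression may have the next course brought forward under 5.2.1 but must leave under 5.2.4. These cannot all be followed, and the conflict needs no assumption about effect size.

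**The case against.** The endpoint agrees with the title and with objective 1.0, so it is not the wrong endpoint. Section 5.1 speaks of initial treatment and then describes the add-on, so it can be read as describing the first step. Section 11.1 is conditional, and no test or decision threshold hangs on it. The 3-cycle rule leaves little room for late responses. No document reports a response after rituximab, and Section 2.1 says rituximab has little single-agent activity in ALL. All of this stands. What remains is a missing breakdown.

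The top of the range in step 3 is also unlikely. It needs every non-responder to receive rituximab, although 5.2.3 makes the add-on optional and two of the first 21 patients died within four weeks.

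Two stronger readings are tempting, and neither is supported. First, a reader might infer that the reported 57% is inflated by rituximab. The documents give no count, and zero is compatible with the text. Second, a reader might note that one reclassified response takes 12/21 to 11/21, whose lower limit of 29.8% falls below the chemotherapy figure of about 30% in 2.4. The plan sets no such criterion, and the crossing is 0.2 points against a rounded number. That number is a CR rate in first salvage, while 12/21 is 5 CR plus 7 CRi with 15 of 21 patients in second salvage or worse. Those differences outweigh one response.

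A pre-rituximab rate has its own bias. CMC-544 continues alongside rituximab, so a response in cycle 3 may be a late CMC-544 response. For add-on patients the split gives roughly a two-course rate, which can understate CMC-544 alone. The fix must say so.

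**Conclusion.** The concern holds as a gap in reporting plus a conflict between rules. The pooled CR/CRi/PR rate is valid for the strategy in Section 1.0, but it does not by itself support the single-agent statement in 11.1, because nothing separates responses first seen after rituximab. Any overstatement is probably a few points and below sampling error. That size rests on my assumed p, f and r; the actual number of such responses is not given. Futility monitoring is unaffected at the observed rates.

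The conflict between 5.2.4 and 5.1, 5.2.1, 5.2.3 and Section 9 is plain on the text. The same patient can be a final failure or a possible later responder, depending on which sentence is followed. Its effect on the rate cannot be calculated from the documents. Both parts should be corrected; neither invalidates the trial.

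**What to change.** 1. Keep the pooled CR/CRi/PR rate as the result for the strategy.
2. In Section 11 add, by schedule and with exact confidence intervals, best response before any rituximab. Count as non-responders on account of the add-on only patients who start rituximab without an earlier CR, CRi or PR; a patient who responded first stays a responder. Label it response before rituximab (about two courses for add-on patients) and note that it can understate CMC-544 alone.
3. List first responses after rituximab separately and descriptively. Base the 11.1 single-agent statement on the pre-rituximab rate, with the pooled rate as its upper bound (assuming that rituximab does not lower response).
4. Amend 5.2.4 so that progression does not remove a patient who is to receive the 5.2.3 add-on after two courses or an early course approved under 5.2.1, and align 9.1 with it.

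The cost is one paragraph and one descriptive table in Section 11, one sentence in 5.2.4 and a matching line in 9.1. Section 7.0 already repeats marrows every 1-2 courses, so response before rituximab can usually be dated from data in hand, including for patients already treated. The rule change mainly affects the last 20 weekly patients. The drawback is small add-on groups: a 20% response in an assumed 5, 10 or 20 patients has exact 95% intervals of 1-72%, 3-56% and 6-44%. The split is descriptive and does not estimate the effect of rituximab.

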## **4.0 Patient Eligibility**

### **4.1 Inclusion Criteria:**

1. Previously treated ALL (including Burkitt's lymphoma and lymphoblastic lymphoma) in relapse or primary refractory. Patients in first relapse will be eligible regardless of the first remission duration. At least 10 patients in Salvage 1-2 will be treated to assess anti-ALL response more precisely.
2. Age 16 years or older. Pediatric patients (<16 years old) will be allowed into the study after safety is established, that is at least 10 adult patients having received 1 or more cycles each.

3. Zubrod performance status 0-3.
4. Adequate liver function (bilirubin  $\leq$  1.5 mg/dL and SGPT or SGOT  $\leq$  3 x upper limit of normal [ULN], unless considered due to tumor), and renal function (creatinine  $\leq$  2 mg/dL). Even if organ function abnormalities are considered due to tumor, the upper limit for bilirubin is  $\leq$  2.0 mg/dL and creatinine  $\leq$  3 mg/dL.
5. Male and female patients who are of childbearing potential agree to use an effective barrier method of birth control (e.g., latex condom, diaphragm, cervical cap, etc.) to avoid pregnancy. Female patients need a negative serum or urine pregnancy test within 14 days of study start (applies only if patient is of childbearing potential. Non-childbearing is defined as  $\geq$  1 year postmenopausal or surgically sterilized).

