## **9.0 Criteria for Removal from the Study**

The Investigator may remove patients from the study for any of the following reasons:

**9.1 Progressive disease.** This is defined as a doubling of the peripheral blasts and an absolute increase of  $> 5 \times 10^9/L$ .

**9.2** Unacceptable adverse events/toxicities (any  $>/=$  grade 3 non-hematologic toxicity that does not at least resolve to < grade 2 or baseline).

**9.3** Investigator thinks a change of therapy would be in the best interest of the patient.

**9.4** If the patient has intercurrent, non-leukemia-related illness that would, in the judgment of the Investigator, affect assessments of clinical status to a significant degree and require discontinuation of protocol therapy.

**9.5** Patient request.

**9.6** Patient is non-compliant with protocol requirements.

The Principal Investigator has the right to terminate this study at any time. Reasons for terminating the study may include, but are not limited to:

**9.7** If the incidence or severity of adverse events indicates a potential health hazard to patients.

**9.8** If the patient enrollment is unsatisfactory.

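### Neither numerical stopping rule looks at toxicity, the 20 added weekly patients have no interim look, and safety for opening to under-16s is defined by adult exposure alone

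*Combined protocol and SAP*

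**What the plan says.** Section 1.0 lists two objectives, efficacy and side effects. Section 11.0 defines the efficacy endpoint: "The primary endpoint for efficacy is response which is defined as CR, CRI or PR". Monitoring is then set out as "The method of Thall [1995] will be employed to perform interim futility monitoring", and the criterion is that if there is "less than a 10% chance that the response rate is 20% or more, we will stop the trial for futility". The prior is beta(1,1). The boundaries are 0/10, 1/17, 2/24, 3/31 and 4/37 responses.

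For the second schedule, section 11.2 states that "it is proposed to treat 20 patients with a weekly schedule of CMC-544, to gain experience with efficacy and toxicity". Its boundaries, 0/7, 1/10, 2/14 and 3/17, again count responses, and it calls the toxicity evaluation descriptive. Section 11.3 adds a further 20 weekly patients, for 40 in all, and gives no boundary or look.

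Section 4.1 lets patients under 16 enter "after safety is established, that is at least 10 adult patients having received 1 or more cycles each".

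Safety also appears in these places:

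- Section 5.2.1 makes the full starting dose for later patients conditional on the absence of safety issues, which it does not define. The first three adults and the first three patients under 16 start at a lower Course 1 dose.
- Section 9.2 allows a patient to be removed for unresolved toxicity of grade 3 or higher.
- Section 9.7 lets the Principal Investigator end the study: "If the incidence or severity of adverse events indicates a potential health hazard to patients".
- Section 10.0 sets out serious adverse event reporting. It also says that only unexpected adverse events go into the case report form.

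**The concern.** A schedule can give a high response rate and still carry an unacceptable rate of severe toxicity. The numerical rules cannot detect that, because they never count toxicity. The gap matters most for the weekly schedule, which section 2.5 introduced part-way through this study and which section 11.3 then extends without any look.

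The condition in 4.1 has a related weakness. It explains what is meant by safety being established, and the explanation is a count of adults dosed. Ten adults who each had a cycle satisfy it whether none or all of them had severe toxicity. The first three of those adults had the lower dose in Course 1. The decision to expose a younger group would then rest on a definition that contains no outcome, observation window or review.

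**Working it through.** **1. Reproduce the plan's own rule.** With r responses in n patients and a beta(1,1) prior, the posterior is beta(1+r, 1+n−r). The rule stops when 1 − BetaCDF(0.20; 1+r, 1+n−r) < 0.10. At 0/10 this is 0.8^11 = 0.086. At 1/17, 2/24, 3/31 and 4/37 it is 0.099, 0.098, 0.093 and 0.099. With one patient fewer, each value exceeds 0.10, so the boundaries are exact. An exact binomial recursion gives early-stopping probabilities of 0.783, 0.240 and 0.045 at response rates 0.1, 0.2 and 0.3. The plan's table states 0.79, 0.24 and 0.044. The futility arithmetic is sound; the gap is what it leaves out.

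**2. How often the response rules stop an active drug.** Section 2.4 reports 12/21 = 57% response. At that true rate the 11.0 rule stops with probability about 0.0002. Section 2.6 reports 8/15 = 53% on the weekly schedule, where the 11.2 rule stops with probability about 0.01. Toxicity enters neither figure.

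**3. The condition in 4.1.** For an assumed severe-toxicity rate q per adult, Pr(3 or more events in 10) is:

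| q | 0.1 | 0.2 | 0.3 | 0.4 | 0.5 |
|---|---|---|---|---|---|
| Pr(≥3 of 10) | 0.07 | 0.32 | 0.62 | 0.83 | 0.95 |

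The condition is met in every case. Even zero events in ten leaves a one-sided 95% upper limit of 1 − 0.05^(1/10) = 26%.

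**4. What a boundary of the same form could do (illustration only).** The documents give no unacceptable toxicity rate, so the limit L and the cut are assumptions. Pause accrual when 1 − BetaCDF(L; 1+x, 1+n−x) > 0.90, where x is the number of patients with an event. For L = 0.30, 4/7 gives 0.942 and pauses; 3/7 gives 0.806 and does not. The boundaries are:

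- Single dose, existing looks: 5/10, 8/17, 10/24, 13/31, 15/37.
- Weekly, existing looks: 4/7, 5/10, 7/14, 8/17.
- Weekly, added looks: 9/20, 11/25, 13/30, 14/35.

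The same recursion, started from the first patient, gives the probability of a pause at L = 0.30:

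| True toxicity rate | 20% | 30% | 40% | 50% |
|---|---|---|---|---|
| Single dose, existing looks | 0.04 | 0.27 | 0.69 | 0.95 |
| Weekly, four existing looks | 0.05 | 0.22 | 0.50 | 0.78 |
| Weekly, with looks added at 20, 25, 30, 35 | 0.06 | 0.29 | 0.69 | 0.94 |

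For other limits with the eight weekly looks: L = 0.20 gives 0.03, 0.30 and 0.75 at true rates of 10%, 20% and 30%. L = 0.40 gives 0.07, 0.29 and 0.67 at 30%, 40% and 50%.

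**The case against.** The strongest reply is that safety is supervised by other means. All serious adverse events go to the IND sponsor's office, life-threatening or fatal ones within 24 hours, and the sponsor forwards events to the FDA. Section 5.3 ties re-treatment to recovery from toxicity. Toxicity was reported at each expansion (sections 2.4 to 2.6), including severe liver enzyme elevations in 2 patients on the weekly schedule. Section 5.2.1 also gives the first three patients under 16 a lower Course 1 dose. All of this stands. A reader might infer that the trial has no safety oversight, or that children would enter without protection; the documents do not support either. They do leave every trial-level decision to judgement, with no event, rate or look named in advance.

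A reader might also infer, from the cited paper's title "Bayesian sequential monitoring designs for single-arm clinical trials with multiple outcomes", that the plan departs from its own method. It does not follow: using a method for a single outcome is not an inconsistency, and nothing here rests on the title.

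Three further points limit what a boundary would achieve:

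- Section 2.6 reports 49 single-dose and 20 weekly patients already treated, so every listed look has passed. Prospective protection comes only from looks added for the extension.
- A boundary at ten adults is a weak filter by itself. With the assumed 30% limit, 5/10 is reached with probability 0.37 at a true 40% and 0.62 at 50%.
- The event in 9.2 has no time window, so it cannot be scored at a fixed look as it stands.

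**Conclusion.** The point holds as an omission that should be corrected, not as evidence that either schedule is too toxic. Both numerical rules ignore toxicity, the 11.3 extension has no look of any kind, and 4.1 equates safety with exposure. No other provision supplies a toxicity criterion that would halt accrual or delay opening to patients under 16.

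That the chance of crossing a toxicity boundary is zero simply restates that there is none. It does not mean that a toxic schedule would certainly run to full size, since 9.7 allows it to be ended. The useful measure is what a boundary would add, and that depends on the assumed limit, the 0.90 cut, the looks, and independent events scored by each look. With a 30% limit and a true rate of 40%, it is 0.69 for single dose, 0.50 with the four weekly looks and 0.69 with eight. None of these settings is a recommendation.

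**What to change.** Add to section 11 a toxicity boundary for each schedule, in the same beta(1,1) posterior form, that pauses accrual for review. Use the existing looks (10, 17, 24, 31, 37 for single dose; 7, 10, 14, 17 for weekly) and state further looks for the 11.3 extension. Looks already passed can be checked against existing records. The investigator and sponsor should set the event, with a fixed scoring window, and the limit. Publish the operating characteristics beside the futility table, including at a true rate equal to the limit.

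Reconcile 4.1 with 5.2.1, so that opening to patients under 16 depends on a review of observed adult toxicity against the sponsor's stated criterion and not on exposure alone.

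The cost is one boundary table, a few added looks, and capture of expected severe events, which section 10.0 keeps out of the case report form. There is also some risk of an unneeded pause. In the illustration with eight weekly looks it is 0.06 when the true rate is 10 points below a 30% limit, and 0.29 when it equals the limit.
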